13.3.4 Analysis of Efficacy Endpoints

Allowing 18 months of follow-up following the last patient accrual, time to next treatment will be estimated by the Kaplan-Meier method. Median time to next treatment will be estimated with 90% confidence intervals. The maximum likelihood estimate of the hazard rate (hazard of next treatment) will be calculated and used to conduct a one-tailed

exponential test at level alpha = .10. This will test the hypothesis that time to next treatment is increased over that expected for olaparib without delay (this assumes the data follow an exponential distribution, otherwise, an alternate parametric test or a one sample log rank test will be used). Toxicities will be summarized by grade, frequency and attribution to olaparib. Median progression-free survival (PFS) and overall survival (OS) will be estimated using the Kaplan Meir method. The Kaplan-Meier method with a log rank test will be applied to test differential response by mutation status. We will estimate the response rate utilizing RECIST and/or GCIG criteria. For those patients with measurable disease and elevated CA125, both RECIST and GCIG criteria will be utilized. For those without measurable disease, GCIG criteria alone will be used to record response. Overall response will be defined as the number of patients with best overall response of CR and PR. The effect of treatment will be reported with its supporting 90% confidence interval.

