1.2. Secondary Objectives and Endpoints

- 1.2.1. To estimate the progression-free survival (PFS) for delayed start olaparib in platinum sensitive recurrent epithelial ovarian cancer with a complete or partial response to last platinum therapy
 - 1.2.1.1. Endpoint: PFS defined as time from enrollment until detected recurrence or progression of disease, via RECISTv1.1, or death from any cause
- 1.2.2. To estimate the overall survival (OS) for delayed start olaparib in platinum sensitive recurrent epithelial ovarian cancer with a complete or partial response to last platinum therapy
 - 1.2.2.1. Endpoint: OS defined as time from enrollment until death from any cause
- 1.2.3. To determine the safety and tolerability for delayed start olaparib in platinum sensitive recurrent epithelial ovarian cancer with a complete or partial response to last platinum therapy
 - 1.2.3.1. Endpoint: Toxicity rates defined by the National Cancer Institute's Common Terminology Criteria for Adverse Events (CTCAE) v5.0
- 1.2.4. To determine the overall response rate of delayed start olaparib in platinum sensitive recurrent epithelial ovarian cancer with a partial response or complete response to last platinum therapy stratified by BRCA mutational status
 - 1.2.4.1. Endpoint: Overall response rate as defined by RECIST v1.1
- 1.2.5. To evaluate the impact of delayed start olaparib in platinum sensitive recurrent epithelial ovarian cancer with a complete or partial response to last platinum therapy on patient reported adverse events
 - 1.2.5.1. Endpoint: Patient reported adverse events as reported by the NCI Patient Reported Outcomes-Common Terminology Criteria for Adverse Events (PRO-CTCAE)
- 1.2.6. To evaluate the impact of delayed start olaparib in platinum sensitive recurrent epithelial ovarian cancer with a complete or partial response to last platinum therapy on quality of life

- 1.2.6.1. Endpoint: Health-related quality of life measured via The Functional Assessment of Cancer Therapy + Ovarian-specific scale (FACT-O)
- 1.2.7. To evaluate the impact of delayed start olaparib in platinum sensitive recurrent epithelial ovarian cancer with a complete or partial response to last platinum therapy on physical functioning
 - 1.2.7.1. Endpoint: Physical function assessed through the PROMIS Physical Function-20a assesses self-reported performance of physical activities

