14. STATISTICAL CONSIDERATIONS

14.1 Study Design/Endpoints

Primary endpoint is defined as the time to next therapy from completion of platinum-based therapy for treatment of recurrence until initiation of post-olaparib treatment. Based on Ledermann et al,²⁹ the expected median time to progression on olaparib following platinum response is 8.4 months for a cohort with 22% *BRCA* mutation prevalence.

Secondary endpoints

Progression-free survival is defined as the time from enrollment until detected recurrence or progression of disease, via RECISTv1.1, or death from any cause.

- Overall survival as defined as the time from enrollment to death from any cause.
- Toxicity rates defined by the National Cancer Institute's Common Terminology Criteria for Adverse Events (CTCAE) v5.0.
- Response rate as defined by RECIST or CA-125 and stratified by *BRCA* mutation status.
- Patient-reported adverse events using the NCI Patient Reported Outcomes-Common Terminology Criteria for Adverse Events (PRO-CTCAE) (See Appendix
- Health-related quality of life measured via The Functional Assessment of Cancer Therapy + Ovarian-specific scale (FACT-O)
- Physical function assessed through the PROMIS Physical Function-20a assesses self-reported performance of physical activities
- Worry and distress measured via Assessment of Survivor Concerns (ASC) Worry Subscale and Impact of Event Scale (IES-R)
- Financial toxicity measured through

a) monetary measure using the Modified Collection of Indirect and Nonmedical Direct Costs (COIN),

b) objective measure of financial burden assessed using Barrera et al.'s Economic Hardship questionnaire⁵¹, and

c) subjective measure of financial distress will be gauged using the Comprehensive Score for Financial Toxicity (COST Measure).

• Exposure measured through quantitating olaparib by LC-MS/MS in a trough sample.

PLANNED ENROLLMENT REPORT

Page 37 of

Racial Categories	Ethnic Cate	Total		
	Not Hispanic or Latino	Hispanic or Latino		
	Female	Female		
American Indian/ Alaska Native	0	0	0	

	Ethnic Cat		
Racial Categories	Not Hispanic or Latino	Hispanic or Latino	Total
	Female	Female	
Asian	3	0	3
Native Hawaiian or Other Pacific Islander	0	0	0
Black or African American	7	0	7
White	65	0	65
More Than One Race	0	0	0
Total	75	0	75

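### Section 13.3.4 names Kaplan-Meier with a log-rank test for response by BRCA status, but the endpoint is a yes/no response rate, and its estimate and interval are not stated to be given by BRCA group

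*Combined protocol and SAP*

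**What the plan says.** Objective 1.2.4 is "To determine the overall response rate of delayed start olaparib in platinum sensitive recurrent epithelial ovarian cancer", in patients with a "partial response or complete response to last platinum therapy stratified by BRCA mutational status". Its endpoint line reads "Endpoint: Overall response rate as defined by RECIST v1.1". The statistical endpoint list in 14.1 has "Response rate as defined by RECIST or CA-125 and stratified by" BRCA mutation status, and the synopsis agrees. No other listed endpoint is stratified by BRCA status.

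Section 13.3.4 then gives, in this order:

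- medians for PFS and OS by Kaplan-Meier;
- the BRCA sentence: "The Kaplan-Meier method with a log rank test will be applied to test differential response by mutation status";
- the response estimate: "We will estimate the response rate utilizing RECIST and/or GCIG criteria";
- its definition: "Overall response will be defined as the number of patients with best overall response of CR and PR";
- the interval: "The effect of treatment will be reported with its supporting 90% confidence interval".

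For the BRCA comparison the plan gives no event, time origin, censoring rule or significance level. It names no comparison of proportions by BRCA group.

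**The concern.** The method and the endpoint do not match. Best overall response of CR or PR is one yes/no value per patient. Kaplan-Meier and log-rank need a time and a censoring status for each patient, and the plan supplies neither for response. The analyst would have to invent a time-to-response endpoint after the data are in, and the result would still describe when responses occur rather than how many patients respond.

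The choice that most needs fixing in advance is what happens to non-responders. If they are censored at progression, they are treated as if they might still have responded later. The Kaplan-Meier complement then exceeds the true response proportion, and by more in the group that progresses faster. The documents expect BRCA-mutated and non-mutated patients to differ in this respect: section 2.2.1 describes higher and longer responses in mutated tumours, and Table 1 shows different PFS by germline BRCA status.

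**Working it through.** **Plan's own figure.** None is given for the BRCA comparison. The group sizes come from 13.2: 75 eligible patients at about 20% BRCA prevalence, so 0.20 × 75 = 15 mutated and 60 not. The 75 itself reproduces:

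- With exponential times, 24 months of accrual and 18 more of follow-up, P(event) = 1 − [exp(−18λ) − exp(−42λ)]/(24λ).
- This is 0.912 at a median of 8 months (λ0 = ln 2/8 = 0.0866) and 0.834 at 11 months (λ1 = ln 2/11 = 0.0630), or 68.4 and 62.6 events.
- Power = Φ{[λ0 − λ1 − 1.282·λ0/√68.4] / (λ1/√62.6)} = Φ(1.28) = 0.90, as stated.

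**Other inputs.** The response rate is 26.2% (16 of 61 evaluable patients, 13.2). Scans on olaparib are every 12 weeks (section 12), which is 2.76 months. Median PFS on a PARP inhibitor is 21.0 months for gBRCA and 9.3 for non-gBRCA (Table 1, niraparib). Response timing and the handling of non-responders are assumptions, because the plan gives neither.

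**Size of the Kaplan-Meier distortion.** Take equal true rates p = 0.262, all responses at the first scan, and non-responders censored at exponential progression with median m. The fraction of non-responders still at risk at that scan is q = 2^(−2.76/m), and the Kaplan-Meier complement is p / [p + (1 − p)q].

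| Median, months | q | Calculation | Kaplan-Meier response |
|---|---|---|---|
| 21.0 | 0.913 | 0.262/(0.262 + 0.738 × 0.913) | 28% |
| 9.3 | 0.814 | 0.262/(0.262 + 0.738 × 0.814) | 30% |
| 18 | 0.899 | 0.262/(0.262 + 0.738 × 0.899) | 28% |
| 4 | 0.620 | 0.262/(0.262 + 0.738 × 0.620) | 36% |
| at risk to data cut-off | 1 | 0.262/1 | 26% |

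Later responses lower q and enlarge the gap.

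**Simulated tests.** All runs use 15 v 60 patients, equal true rates of about 26% and a two-sided 0.05 level.

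| Scenario | Kaplan-Meier response | Log-rank rejects |
|---|---|---|
| 21.0 v 9.3 months, censored at progression | 27-29% v 28-33% | about 5-6% |
| 18 v 4 months, later responses, censored at progression | 29% v 45-46% | about 10-12% |
| Non-responders at risk to cut-off, same response timing | about 26% in both | 4-5% |
| Responses early in mutated, late in non-mutated patients; same progression | not tabulated | 8-13% |

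Fisher's exact test on the proportions rejected in 2.6% to 4.4% of trials in equal-rate scenarios (true rates 26% to 50%). Its power with 15 v 60 is low: about 0.32-0.33 for 40% v 20%, and 0.59-0.60 for 50% v 20%.

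**Precision of per-group rates** (exact 90% limits). 4/15 gives 10% to 51%, and 16/60 gives 17% to 38%. Both assume that all 75 patients are evaluable for response.

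**The case against.** The strongest reply is that the sentence concerns PFS and OS. It directly follows the sentence on their medians and comes before the response rate is introduced, so the word response may be loose usage for outcome. On that reading the log-rank test is the standard choice and the distortion above does not arise. This reading is possible and cannot be excluded. It does not remove the need for an edit: the endpoint lists stratify response by BRCA status, not PFS or OS, and the per-group response rate would still be unstated. Reading the sentence as duration of response does not help either. Section 12.1.5 defines that quantity, but it is not a listed endpoint and it concerns responders only.

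Two stronger readings are tempting, and the documents do not support them.

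- *Objective 1.2.4 has no analysis.* Section 13.3.4 does plan a response rate with a 90% interval, and the objective is one of estimation, so no between-group test is required. What is missing is the statement that the estimate and interval are given by BRCA group.
- *The planned test will produce false positives.* No section says that non-responders are censored at progression. With the only BRCA-split medians on a PARP inhibitor in the documents, rejection stays near 5%. The 18 and 4 months are not document figures for these groups, and 4 months is close to the 3.9 months of the placebo arm among non-gBRCA patients in Table 1.

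**Conclusion.** The point holds as a mismatch between endpoint and method. As written, the only BRCA comparison named for response uses a test of timing on an endpoint that has no time, so objective 1.2.4 is not addressed by it. On the PFS/OS reading, the gap is that the response rate and interval are not assigned to BRCA groups and no comparison of rates is planned.

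This conclusion does not depend on inflated error rates. If non-responders are censored at progression, the Kaplan-Meier complement overstates response by about 1 to 7 points under the documents' medians (27-29% and 28-33% against 26%). Material false-positive inflation needs either a strong contrast in progression or different response timing in the two groups. There is none when non-responders stay at risk to data cut-off and timing is the same. All these sizes rest on assumed response timing and exponential progression, and on Table 1 medians for another PARP inhibitor.

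The effect is confined to one secondary comparison with no stated power. The sentence should be corrected before analysis.

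**What to change.** In 13.3.4:

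1. Report the response rate with an exact 90% confidence interval separately for BRCA-mutated and non-mutated patients who are evaluable for response, and a 90% interval for the difference. Fisher's exact test may be added, with its low power acknowledged.
2. Restrict the Kaplan-Meier and log-rank sentence to time to next therapy, PFS and OS by BRCA status, and name those endpoints.
3. If expected precision is stated, give 10% to 51% (4/15) and 17% to 38% (16/60) as a best case. Section 12 says that not all patients will have measurable disease, and 12.1.1 limits who is evaluable, so actual intervals will be wider.

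The cost is a rewording of one or two sentences of the plan. No new data are needed, because BRCA testing is already required by 3.1.3.

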13.3.5 Analysis of Patient Reported Outcomes, Quality of Life and Financial Toxicity Endpoints

Additional **Secondary Endpoints** include a series of quality of life instruments and financial toxicity measures. These instruments will be administered starting at onset of trial enrollment and periodically thereafter. Patient reported adverse events, worry and distress (3 instruments measured every 4 weeks), health related quality of life, physical functioning and financial toxicity (5 instruments measured every 12 weeks) will provide data for longitudinal analysis with mixed effects linear models. We will focus on change over time particularly between the two treatment periods, pre and post olaparib. Our linear mixed effects models will emphasize random coefficients that allow non-linear profiles, typically polynomial regression, restricted cubic splines or piecewise linear splines with a knot to represent the time of starting olaparib. These models will permit us to estimate whether quality of life and financial toxicity change over the course of the clinical trial and, in particular, whether the observed change suggests a shift that is consistent with the start of olaparib therapy.

For drug exposure measured through quantitating olaparib by LC-MS/MS in a trough sample, trough concentrations between groups will be compared with non-parametric Wilcoxon signed rank test with significance set at P<0.05. If significant, we may explore ROC analyses.

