6.2.2. Supportive care

No routine prophylactic medications are indicated at the start of therapy. In general, the use of any concomitant medication/therapies deemed necessary for the care of the patient are allowed with the exceptions noted in 6.2.1

6.3. **Duration of Therapy**

Patients will be enrolled continuously to the study. Patients will continue evaluation and treatment until one of the following criteria applies:

- Disease progression per RECIST v1.1³⁹
- Unacceptable adverse event(s) defined as any grade 3 or 4 adverse event, per National Cancer Institute's Common Terminology Criteria for Adverse Events (CTCAE) v5.0 or PRO-CTCAE, that does not resolve to grade ≤ 1 within 28 days after onset.
 - Treatment will be interrupted for any grade 3 or 4 event related to treatment. If the toxicity resolves entirely or to grade 1, treatment will be restarted with a dose reduction. If the event does not resolve within 4 weeks or if two previous treatment interruptions with subsequent dose reductions occur, the patient will be withdrawn.
- Patient withdraws consent.
- Development of second malignancy (except for basal cell carcinoma or squamous cell carcinoma of the skin) that requires treatment, which would interfere with this study.
- Intercurrent illness that prevents further administration of treatment
- General or specific changes in the patient's condition render the patient unacceptable for further treatment in the judgment of the investigator.

6.4. **Duration of Follow Up**

Patients will be followed until the initiation of the next therapy post olaparib treatment. Each patient, regardless of reason for removal from study, will have at least 18 months follow up relative to time of enrollment. Secondary efficacy endpoints will be tracked after official follow-up has been completed.

Assessments in follow up:

- Office visit or review of medical records every 3 months
- Survival endpoints both progression free survival (PFS) and overall survival (OS)

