11. STUDY CALENDAR

Baseline evaluations are to be conducted within 14 days prior to start of trial. Imaging CT scans and x-rays must be done ≤ 4 weeks prior to the start of therapy.

Procedure/Test	Pre- Study	Surveillance every 4 weeks	Day 1 of each cycle	Every 12 weeks	30 day follow- up*	Every 3 months
Informed consent	Х					
Demographics	Х					
Concurrent medications	Х	Х	Х		Х	
Medical history	Х					
Physical exam ^A	Х	Х	Х		Х	
Vital signs ^A	Х	Х	Х		Х	
Height and Weight ^A	Х	Х	Х		Х	
Performance status ^A	Х	Х	Х		Х	
CBC w/diff, platelets A	Х		Х		Х	
Serum chemistry A,B	Х		Х		Х	
CA125 ^A	Х	Х	Х		Х	
PTT/PT/INR ^C	Х					
EKG ^C	Х					
Tumor Measurements D	Х			Х		
Baseline signs & symptoms	Х					
Adverse event evaluation ^E	Х	Х	Х		Х	
Worry and Distress Measures ^F	Х	Х	Х		Х	
Quality of Life and Physical Function Measures ^G	Х			Х	Х	
Financial Toxicity Measures ^H	Х			Х	Х	
Urine or serum B-HCG for WOCBP ¹	X					
Tissue Collection ^J	Х				Х	
PK plasma sample ^K			ХК			

BRCA testing ^L	X			
Survival Follow-up ^M				Х

*Patients should be seen 30 days after completion of treatment to assess for resolution of toxicity

- A. These procedures do not need to be repeated in cycle 1 if done pre-study within 7 days prior to start of protocol therapy.
- B. Albumin, alkaline phosphatase, total bilirubin, direct bilirubin, bicarbonate, BUN, calcium, chloride, creatinine, glucose, potassium, total protein, SGOT [AST], SGPT [ALT], sodium, magnesium, phosphorus
- C. Required pre-study, then as clinically indicated
- D. Prior to olaparib initiation, imaging will only be done for doubling of nadir CA125 or per physician discretion for patient symptoms. Following initiation of olaparib, CT scans will be obtained every 12 weeks as part of surveillance. CT scans can be obtained for rising CA125 or physician preference for patient symptoms before scheduled routine surveillance.
- E. Adverse event evaluation will include both the CTCAE and the PRO-CTCAE (See Appendix D).
- F. Worry and distress measured via Assessment of Survivor Concerns (ASC) (See Appendix E) worry subscale and Impact of Event Scale (IES-R) (See Appendix F).
- G. Health-related quality of life will be measured via The Functional Assessment of Cancer Therapy + Ovarian-specific scale (FACT-O) (See Appendix G) and physical function assessed through the PROMIS Physical Function-20a assesses self-reported performance of physical activities (See Appendix H).

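### The two-period model in 13.3.5 has no place for the off-drug 30-day questionnaires, which then fall in the post-olaparib segment and can bias the estimated shift in either direction

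*Combined protocol and SAP*

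**What the plan says.** **Analysis.** Section 13.3.5 of the combined protocol and SAP plans linear mixed models for two groups of instruments: "3 instruments measured every 4 weeks" (PRO-CTCAE, ASC worry, IES-R) and "5 instruments measured every 12 weeks" (FACT-O, PROMIS physical function, COIN, Economic Hardship, COST). The emphasis is stated as: "We will focus on change over time particularly between the two treatment periods, pre and post olaparib". The candidate forms are polynomial regression, restricted cubic splines, or "piecewise linear splines with a knot to represent the time of starting olaparib". The result is to be read as showing "whether the observed change suggests a shift that is consistent with the start of olaparib therapy".

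**Calendar.** In Section 11, the 30-day follow-up column is marked for adverse event evaluation (which includes PRO-CTCAE), for worry and distress, for the "Quality of Life and Physical Function Measures" and for the financial measures. The note under the grid fixes the timing: "Patients should be seen 30 days after completion of treatment to assess for resolution of toxicity".

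**Why treatment ends.** Section 6.3 says "Patients will continue evaluation and treatment until one of the following criteria applies" and then lists RECIST progression, unresolved grade 3 or 4 events, withdrawal of consent, second malignancy, intercurrent illness and investigator judgment. Section 10 expects resistant disease eventually in everyone except those who leave for toxicity or withdraw consent.

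**What is absent.** Section 13.3.5 does not mention the 30-day form. It has no term for stopping olaparib or for progression, and no rule that sets this form apart.

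**The concern.** The quantity of interest is a change at the start of olaparib. A form completed 30 days after the last dose describes a patient who is off the drug and who has usually just progressed or stopped for toxicity. A model with two periods and one knot at the start can place that form only after the knot. Whatever changed because olaparib stopped, or because of the reason it stopped, is then averaged into the period meant to describe olaparib.

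The error can go either way. Worsening after progression would look like a harmful shift. Recovery after a toxicity stop, which is what the visit is there to assess, would offset real harm on treatment.

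Objectives 1.2.5 to 1.2.9 rest on this model, and the rationale (Section 2.4) includes better quality of life and lower financial toxicity in the trial's hypothesis.

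**Working it through.** The plan gives no effect size, SD or power for these endpoints, so there is no figure of its own to reproduce. Time on olaparib after a delayed start is not stated either; it is assumed below.

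**1. How many post-start records are off drug?**

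Inputs: form intervals c = 84 and 28 days (13.3.5); one 30-day form per patient (Section 11). Assumptions: exponential time on drug with median 4, 6 or 8 months, every patient stops, and every 30-day form is completed. The mean is μ = median × 30.44 / ln 2 = 175.6, 263.5 or 351.3 days.

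*Form schedule restarts at olaparib start.* The expected number of on-drug forms is q/(1−q), with q = exp(−c/μ). The off-drug share is 1/[1 + q/(1−q)] = 1 − q.

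| Median on drug | 12-weekly, 1 − exp(−84/μ) | 4-weekly, 1 − exp(−28/μ) |
|---|---|---|
| 4 months | 38% | 15% |
| 6 months | 27% | 10% |
| 8 months | 21% | 8% |

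Under this clock 1 − q is also the chance of stopping before the first on-drug form, so for the same 38%, 27% or 21% of patients the 30-day form is the only 12-weekly record after the start.

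*Form schedule runs from enrolment.* With olaparib starting at a random point in the 12-week interval, the expected number of on-drug forms is μ/84 = 2.09, 3.14 or 4.18. The share is 1/(1 + μ/84) = 32%, 24% or 19%. The 30-day form is the only post-start record for 1 − (μ/84)(1 − q) = 21%, 14% or 11%.

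*Extreme case: every stop falls on a 12-weekly scan date that is also a form date.* The share is (1 − q)/(2 − q) = 0.380/1.380, 0.273/1.273 and 0.213/1.213, or 28%, 21% and 18%. No patient then has the 30-day form as the only record.

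*Fixed durations as a cross-check.* At 3, 6 and 8.4 months on drug, the 12-weekly share is 1 of 2 (50%), 1 of 3 (33%) and 1 of 4 (25%). Counting the day-1 form as well, the 4-weekly share is 20%, 13% and 9%.

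**2. How far does this move the estimate if olaparib has no effect?**

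Expected generalised least squares estimate from a random-intercept model. Assumptions: intraclass correlation 0.5, median time to olaparib start about 5 months where it is not capped, exponential time on drug with median 5 or 8.4 months, no change on drug, and a worsening of 0.3 to 0.8 SD at the 30-day visit only.

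| Model | Instruments | 30-day form pooled after start | Separate off-treatment term |
|---|---|---|---|
| Pre/post level | 12-weekly | −0.04 to −0.23 SD | 0.00 |
| Pre/post level | 4-weekly | −0.01 to −0.08 SD | 0.00 |
| Slope after knot | 12-weekly | −0.07 to −0.23 SD per year | 0.00 |
| Slope after knot | 4-weekly | −0.04 to −0.13 SD per year | 0.00 |

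The estimator is linear in the data, so an improvement of the same size at that visit gives the same values with the opposite sign.

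**3. How often would this produce a false positive?**

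Simulated trials of 75 patients on a 12-weekly form, with no on-drug effect, between-patient SD 15, residual SD 9, median 6 months on drug, and a 10-point fall confined to the 30-day visit:

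- A plain pre/post level contrast gave about −3.7 points with p<0.05 in 97-99% of trials. With an enrolment clock this was −3.0 points and 89%, and with scan-timed stops −2.6 points and 81%.
- The slope after a knot at olaparib start, which is a form 13.3.5 names, rejected in about 15-24%.
- Smaller falls under the level contrast: 5 points gave −1.8 and 52%; 3 points gave −1.1 and 28%.
- Coding the visit separately brought rejection back to 4-9%.

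**The case against.** **13.3.5 does not say these forms are on-olaparib time.** This is correct. The section names only the 4-weekly and 12-weekly schedules and gives the 30-day form no code. A reader might infer that the plan deliberately counts it as treatment time; the text does not support that. What stands is narrower: the calendar collects the form, and the only stated model offers it no place except after the start.

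**Contamination by the next therapy.** A reader might infer that post-olaparib therapy is also being read as an olaparib effect. The documents do not show this. Section 6.2.1 requires withdrawal before other anticancer agents are given, and Section 6.6 ends on-study time when post-olaparib therapy starts (or 30 days after removal for an adverse event). Neither expressly cancels the visit, but nothing places questionnaires after the next therapy begins. The point does not need it.

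**A near-certain false positive.** The 97-99% is tempting as a headline. It requires a 10-point fall in all patients and a plain level contrast. The words on two periods and a shift leave room for such a contrast, but it is not among the listed forms. The named knot model is far less sensitive, and the flexible curves may absorb some late change, though without separating it from olaparib.

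**Treatment-policy reading.** The objectives concern the impact of a delayed-start strategy, for which records after stopping are legitimate. That holds for a whole-course summary but not for the shift at olaparib start that 13.3.5 sets out to estimate. Reporting both analyses meets it.

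**Recall windows differ.** This stands and shapes the remedy. PRO-CTCAE, IES-R and FACT-O look back 7 days and the COIN costs look back one month, so at this visit they are essentially off drug. Most Economic Hardship items look back 3 months, of which about 60 of 90 days can be on drug.

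**Conclusion.** The point holds as an unaddressed gap with a directional risk. The 30-day forms are off drug and usually follow progression or toxicity. Section 13.3.5, with two periods and one treatment-linked knot at the start, leaves them in the post-olaparib segment. The estimated shift can be biased towards apparent harm or towards masking it.

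For median time on drug of 4 to 8 months, the forms are roughly 20-40% of post-start records for the 12-weekly instruments (19-38% across the two form clocks) and about 8-15% for the 4-weekly ones. Patients still on olaparib at the analysis and missing 30-day forms would lower these shares. The induced shift under the level model is about 0.04 to 0.23 SD for the 12-weekly instruments and 0.01 to 0.08 SD for the 4-weekly ones, so it is material mainly for the former. Its size depends on the assumed change at that visit and on the model form.

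These are secondary endpoints in a single-arm trial, and the primary endpoint is unaffected. Label: cheap improvement.

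**What to change.** In 13.3.5:

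1. Define the olaparib segment as first dose to last dose.
2. Give the 30-day form its own off-treatment indicator, or leave it out of the pre/on-olaparib contrast and report it separately.
3. Assign each instrument by its recall window. The Economic Hardship items that look back 3 months are still largely on drug at this visit and should not be coded as off-treatment automatically. That form's two forward-looking items need their own rule.
4. Report a sensitivity analysis with the 30-day forms pooled into the post-start segment. This also serves readers who prefer the treatment-policy view.

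The cost is a few sentences and one indicator variable, with no change to visits, forms or treatment. Slightly fewer records inform the on-olaparib segment. One limit remains: decline just before olaparib stops stays in the on-drug segment, and the report should say so.
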